### **Determination of the arm with the highest blood pressure**

At Visit 1 (week -4), seated BP should be measured in both arms after 5-minute rest period, and then again after 1 minute in both arms in seated position. The arm with the highest SBP will be determined at this visit, and BP should be measured in this arm throughout the study.

### **Measurement Technique (22)**

At Visit 1, immediately following arm selection, with the patient in the same position, an additional seated BP should be measured in the selected arm (at least 1 minute after last measurement).

[figure not shown]
At all other on-site visits, following the 5-minute rest period, 3 separate seated BPs should be measured in the arm selected at Visit 1, with at least 1 minute between BP measurements and with the cuff fully deflated between measurements.

All 3 BPs will be recorded in the patient's e-CRF. The mean of the 3 seated BPs will constitute the BP value for that visit.

Three seated pulse rate measurements will also be obtained. The mean of the 3 seated pulse rate measurements will constitute the pulse rate value for that visit.

## Appendix D General guidance for the follow-up of laboratory abnormalities by Sanofi

### NEUTROPENIA

[figure not shown]

#### Note:

- The procedures described in the above flowchart are to be discussed with the patient only in case the event occurs. If applicable (according to local regulations), an additional consent (e.g., for HIV testing) will only be obtained in the case the event actually occurs.
- For individuals of African descent, the relevant value of concern is <1000/mm^3

Neutropenia is to be recorded as an AE only if at least 1 of the criteria listed in the general guidelines for reporting AEs in [Section 10.4.2](#) is met.

[figure not shown]
### THROMBOCYTOPENIA

**Note:**

The procedures above flowchart are to be discussed with the patient only in case described in the the event occurs. If applicable (according to local regulations), an additional consent (e.g., for HIV testing) will only be obtained in the case the event actually occurs.

Thrombocytopenia is to be recorded as an AE only if at least 1 of the criteria listed in the general guidelines for reporting AEs in [Section 10.4.2](#) is met.

[figure not shown]

- In ANY CASE, FOLLOW** the instructions listed in the box below:
1. **INFORM** the Site Monitor who will forward the information to the Study Manager
  2. **INVESTIGATE** specifically for malaise with or without loss of consciousness, dizziness, and/or hypotension and/or episode of arrhythmia in the previous 72 hours; rule out muscular injury
  3. **PERFORM** the following tests:
    - LFTs: AST, ALT, alkaline phosphatase, total and conjugated bilirubin and prothrombin time / INR
    - CPK, serum creatinine, complete blood count
    - Anti-HAV IgM, anti-HBc IgM (HBV-DNA if clinically indicated), anti-HCV and HCV RNA, anti-CMV IgM and anti-HEV IgM antibodies
    - Depending on the clinical context, check for recent infection with EBV, herpes viruses, and toxoplasma
    - Hepatobiliary ultrasonography (or other imaging investigations if needed)
  4. **CONSIDER** Auto-antibodies: antinuclear, anti-DNA, anti-smooth muscle, anti-LKM
  5. **CONSIDER** consulting with hepatologist
  6. **CONSIDER** patient hospitalisation if INR>2 (or PT<50%) and/or central nervous system disturbances suggesting hepatic encephalopathy
  7. **MONITOR** LFTs after discontinuation of IMP:
    - As closely as possible (or every 48 hours) until stabilization, then every 2 weeks until return to normal/baseline or clinical resolution.
  8. **FREEZE** serum sample (5ml x 2)

\*If unable to re-test in 72 hours, use original lab results to decide on further reporting/monitoring/discontinuation.  
Note:

[figure not shown]
- “Baseline” refers to ALT sampled at Baseline Visit; or if Baseline value unavailable, to the latest ALT sampled before the Baseline Visit. The algorithm does not apply to the instances of increase in ALT during Screening.
- See [Section 10.4](#) for guidance on safety reporting.
- Normalization is defined as ≤ULN or Baseline value, if Baseline value is >ULN.

### ACUTE RENAL FAILURE

Acute renal failure is to be recorded as an AE only if at least 1 of the criteria listed in the general guidelines for reporting AEs in [Section 10.4.2](#) is met.

### SUSPICION OF RHABDOMYOLYSIS

Suspicion of rhabdomyolysis is to be recorded as an AE only if at least 1 of the criteria in the general guidelines for reporting AEs in [Section 10.4.2](#) is met.

# EFC148387 Amended Protocol 01

1 OVERVIEW AND INVESTIGATIONAL PLAN

1.1 STUDY DESIGN AND RANDOMIZATION

This is a Phase 3, multicenter, randomized, double-blind, placebo-controlled, parallel-group study.

The study comprises a Screening phase of up to 2 weeks and a subsequent 2-week single-blind placebo Run-in phase, a 26-week double-blind treatment period, a 26-week double-blind extension period, and a 4-week post-treatment follow-up period. Patients who prematurely discontinue the study treatment are expected to continue in the study.

Approximately 780 patients (260 per treatment group) will be randomized centrally via Interactive Response Technology (IRT) in a 1:1:1 ratio to 1 of the 3 treatment groups:

- Sotagliflozin 400 mg.
- Sotagliflozin 200 mg.
- Placebo.

Randomization will be stratified by:

- Hemoglobin A1c (HbA1c) at Screening ($\leq 8.5\%$ and $> 8.5\%$).
- Mean systolic blood pressure (SBP) at Screening (< 130 mmHg and ≥ 130 mmHg).
- Chronic kidney disease (CKD) stage (3A, 3B) based on Screening estimated glomerular filtration rate (eGFR).

1.2 OBJECTIVES

1.2.1 Primary objectives

The primary objective of this study is to demonstrate the superiority of sotagliflozin 400 mg and 200 mg versus placebo with respect to HbA1c reduction at Week 26 in patients with Type 2 diabetes (T2D) who have inadequate glycemic control and moderate renal impairment.

1.2.2 Secondary objectives

The secondary objectives of this study are:

- To assess the effects of sotagliflozin 400 mg and 200 mg versus placebo, based on:
 - Change from Baseline in fasting plasma glucose (FPG) at Week 26,
 - Change from Baseline in body weight at Week 26,
 - Change from Baseline in SBP at Week 12 for patients with Baseline SBP ≥ 130 mmHg,
 - Change from Baseline in SBP at Week 12 for all patients,
 - Percentage change in urine albumin:creatinine ratio (UACR) from Baseline to Week 26 (for patients with Baseline UACR > 30 mg/g),
 - Proportion of patients with HbA1c $< 6.5\%$, $< 7.0\%$ at Week 26.

- To evaluate the safety of sotagliflozin 400 mg and 200 mg versus placebo over the 52 weeks of treatment.

1.2.3 Other objectives

Other objectives of this study are to compare sotagliflozin 400 mg and 200 mg versus placebo with respect to:

- Change from Baseline in SBP at Weeks 26 and 52 for patients with Baseline SBP ≥ 130 mmHg.
- Change from Baseline in SBP at Weeks 26 and 52 for all patients.
- Change from Baseline in HbA1c at Week 52.
- Change from Baseline in FPG at Week 52.
- Change from Baseline in body weight at Week 52.
- Change from Baseline in eGFR.
- Change from Baseline on the following endpoints:
 - Cystatin C,
 - Urinary glucose excretion (UGE),
 - Urine glucose:creatinine ratio (UGCR),
 - Fructosamine,
 - N-terminal prohormone of brain natriuretic peptide (NT-proBNP).
- Progression of kidney disease, based upon changes in eGFR or albuminuria.
- Change from Baseline to Week 12 SBP for patients with Baseline SBP < 130 mmHg.
- Change from Baseline to Week 12 diastolic blood pressure (DBP) for all patients and the subset of patients with Baseline DBP ≥ 80 mmHg.
- The proportion of patients requiring rescue for hyperglycemia during 26-week double-blind treatment period.
- To assess plasma levels of sotagliflozin and sotagliflozin-3-O-glucuronide in the sotagliflozin treatment arms.

1.3 DETERMINATION OF SAMPLE SIZE

[figure not shown]
The sample size/power calculations were performed based on the primary endpoint. Assuming a common standard deviation (SD) of 1.2% and using a 2-sided test at a 0.05 α -level, 130 patients in each CKD stratum (3A or 3B) in each treatment group will provide the following power:

- To detect a treatment difference of 0.6% in mean HbA1c change from Baseline to Week 26 between sotagliflozin 400 mg versus placebo:
 - 98% power comparing sotagliflozin 400 mg versus placebo in patients in CKD 3A stratum,
 - 98% power comparing sotagliflozin 400 mg versus placebo in patients in CKD 3B stratum,

- 99% power comparing sotagliflozin 400 mg versus placebo in overall patient population.
- To detect a treatment difference of 0.5% in mean HbA1c change from Baseline to Week 26 between sotagliflozin 200 mg versus placebo:
 - 91% power comparing sotagliflozin 200 mg versus placebo in patients in CKD 3A stratum,
 - 91% power comparing sotagliflozin 200 mg versus placebo in patients in CKD 3B stratum,
 - 99% power comparing sotagliflozin 200 mg versus placebo in overall patient population.
- At least 80% overall power to have all 6 above statistical inferences statistically significant based on above treatment effect assumptions.

1.4 STUDY PLAN

The study plan is presented graphically as follows.

The study flowchart can be found in Appendix E.

1.5 MODIFICATIONS TO THE STATISTICAL SECTION OF THE PROTOCOL

This section summarizes major changes to the protocol statistical section with emphasis on changes after study start (after the first patient was enrolled).

The protocol history table below gives the timing, rationale, and key details of major changes to the protocol statistical section.

The first patient was enrolled on September 13, 2017. The study analysis will be conducted in 2 steps. The first step analysis is planned when all patients have been randomized and have their data at the minimum up to Week 26 collected and validated. The second step will be conducted at the end of the study.

Table 1 - Protocol amendment statistical changes

Amendment Number	Date Approved	Rationale	Description of statistical changes
1	20-Dec-2017	Baseline eGFR defined as recommended by CDISC Therapeutic Area Data Standards User Guide for Diabetic Kidney Disease	For serum creatinine and eGFR, the baseline value is defined as the average of all values before the first dose of double blind IMP for those randomized and exposed or before randomization for those who were randomized but never exposed to IMP
1	20-Dec-2017	Urgent coronary revascularization not adjudicated by CEC to be consistent with outcome trials	Urgent coronary revascularization not included in adjudication related analyses
1	20-Dec-2017	To be consistent with other studies in the SOTA program	Addition of femoral neck as a region for the bone mineral density (BMD) assessments
1	20-Dec-2017	The effect in body weight is considered more closely associated with the planned indication	Change in the order of secondary objectives and endpoints for the study
1	20-Dec-2017	5 half-lives of sotagliflozin prolonged to 10 days considering patients with moderate renal dysfunction	5 half-lives of IMP updated from 5 days to 10 days; TEAE period updated accordingly

1.6 STATISTICAL MODIFICATIONS MADE IN THE STATISTICAL ANALYSIS PLAN

The statistical analysis plan history table below gives the timing, rationale, and key details for major changes to the statistical analysis features in the statistical analysis plan. Changes also incorporated in a protocol amendment are cross-referenced to [Table 1](#).

Table 2 - Statistical analysis plan statistical changes

SAP version number	Date approved	Rationale	Description of statistical changes
1	10-Oct-2018	Baseline eGFR defined as recommended by CDISC Therapeutic Area Data Standards User Guide for Diabetic Kidney Disease	Baseline eGFR defined as recommended by CDISC Therapeutic Area Data Standards User Guide for Diabetic Kidney Disease ^a
1	10-Oct-2018	Urgent coronary revascularization not adjudicated by CEC to be consistent with outcome trials	Urgent coronary revascularization not included in adjudication related analyses ^a
1	10-Oct-2018	To be consistent with other studies in the SOTA program	Addition of femoral neck as a region for the bone mineral density (BMD) assessments ^a
1	10-Oct-2018	The effect in body weight is considered more closely associated with the planned indication	Change in the order of secondary objectives and endpoints for the study ^a
1	10-Oct-2018	Clarification on EOSI renal events	Details specified on renal events to be consistent with outcome studies in Section 2.1.4.2
1	10-Oct-2018	Clarification on ESRD	ESRD is defined in 2.4.4.3 consistent with CEC charter
1	10-Oct-2018	[REDACTED]	[REDACTED]
1	10-Oct-2018	[REDACTED]	[REDACTED]
1	10-Oct-2018	Updating the wording to be consistency with CEC charter	"Unstable angina leading to hospitalization" changed to "Unstable angina requiring hospitalization"
2	20-May-2019	[REDACTED]	[REDACTED]
2	20-May-2019	Number of iterations for multiple imputation was changed	Number of iterations for multiple imputation was changed from 10 000 to 2000
2	20-May-2019	Wording change to be consistent with CEC charter	"Heart failure leading to hospitalization" changed to "Heart failure requiring hospitalization"

Statistical Analysis Plan

Version: Final 3.0
Lexicon Pharmaceuticals Protocol No. EFC14837

Date of Issue: 21 November 2019
Covance Study ID:000000155205

SAP version number	Date approved	Rationale	Description of statistical changes
2	20-May-2019	MedDRA version and dictionary updated	MedDRA version was updated to v21.1 and list of PTs for selected EOSI were updated
3	This version	Change in study Sponsor led to a strategic decision not to report the first step analysis in a standalone CSR	First step analyses will be combined with the second step analysis and both will be conducted at the end of the study in a single CSR The following sections/paragraphs are not applicable Section 2.4.4.4 – the last paragraph Section 3. – the first step analysis details Section 4. – the first data base lock
3	This version	[REDACTED]	[REDACTED]
3	This version	Assess robustness of the ITT-based analyses	Identify possible need to conduct sensitivity analyses for PK anomalies
3	This version	Provide comparative analyses at Week 52 for the primary and secondary efficacy endpoints to further characterize the long-term effects of sotagliflozin	Apply statistical methods specified in Sections 1.6, 2.4.4.1, and 2.4.4.2 to the primary and secondary endpoints at Week 52
3	This version	Based on clinical guidelines for a higher A1C target for patients with chronic kidney disease	Add another endpoint:of proportion of patients with HbA1c <8%, at Week 26 and Week 52

a Change made in Protocol Amendment 1 dated 20-Dec-2017.

The first step analysis was conducted and reported for top line results; it was not used to inform a standalone Clinical Study Report (CSR) limited to just the 6-month data. A single CSR will be written for this study and will include the results coming from the analyses specified at both the first and second steps (see Section 3 of this SAP for more details).

The statistical methods detailed in this section will be performed in addition to those specified in other sections of the SAP. The majority of these additional assessments will serve as sensitivity analyses and will be used to support/qualify the robustness of results from the originally planned analyses.

The primary and continuous secondary efficacy endpoints for the overall population (combined CKD stages 3A and 3B) or in the individual group of CKD stage 3A and 3B patients, missing data at Week 26 (or Week 12 for SBP) visit will be imputed using a model built separately in each treatment group and estimated from the patients in the same treatment group who prematurely discontinue the IMP before the Week 26 (or Week 12 for SBP) visit but have the measurement for the endpoint (ie, retrieved dropouts). The imputation model will include the randomization strata and the corresponding baseline value. In cases of non-convergence during the imputations, the offending stratum will be identified and then will be dropped from the model. Considering that the number of retrieved dropout patients in each treatment group is expected to be small, a simple imputation model based on regression will be used with baseline measurement included as the predictor.

An alternative (back-up) imputation method will be used if the number of patients who prematurely discontinue the IMP before the Week 26 (or Week 12 for SBP) visit but have the measurement for the endpoint is < 5 in any treatment groups (ie, an insufficient number of retrieved dropouts to support the imputation method described above). This criterion will be assessed for each primary or continuous secondary efficacy endpoint.

In the back-up imputation method, missing post-baseline endpoint values at Week 26 (or Week 12 for SBP) will be imputed by the washout Multiple Imputation (MI) method under the missing not at random (MNAR) framework.

Missing endpoint data at the Week 26 (or Week 12 for SBP) in all treatment groups (sotagliflozin 400 mg, 200 mg and placebo) are imputed from a model estimated from patients in the placebo group who have the endpoint data available.

For patients in the sotagliflozin 400 mg and 200 mg group with missing data at Week 26 (or Week 12 for SBP), their missing values will be imputed using observed baseline and the observed primary endpoint data from placebo completers; no intermittent values from either placebo or the active treatment groups will be used.

For placebo patients, missing data will be imputed based on the placebo group data. Intermittent observed values will be used while imputing missing values at Week 26 (or Week 12 for SBP). In cases that a non-monotone missing data pattern occurs at the intermediate visits, these data points will be first imputed in the placebo group using the Markov Chain Monte Carlo (MCMC) option in PROC MI to achieve a monotone missing pattern for all placebo patients. The Week 26 (or

Week 12 for SBP) endpoint values will be subsequently imputed from the multiple copies of the original dataset where each copy will have a monotone missing pattern.

The imputation models for the washout MI method will include the randomization strata and the corresponding baseline value. Missing data will be imputed using the regression method. In cases of non-convergence during the imputations, especially for the MCMC application in the placebo non-monotone datasets, graphical measures (eg, trace and autocorrelation plots) will be used to identify the offending variable and once detected, that variable(s) will be dropped from the model and the imputations will be re-run. These re-run models will use the same seed number and number of imputations as used in the original models.

For the overall population (combined CKD stages 3A and 3B) each of the completed datasets after the imputation will be analyzed using the Analysis of Covariance (ANCOVA) model with treatment groups (sotagliflozin 400 mg, 200 mg and placebo), randomization stratum of HbA1c ($\leq 8.5\%$, $> 8.5\%$), randomization stratum of CKD stage (3A, 3B), randomization stratum of SBP (< 130 mmHg, ≥ 130 mmHg), and country as fixed factors, and baseline HbA1c value as a covariate.

For each CKD (3A, 3B) stratum, each of the complete datasets will be analyzed by an Analysis of Covariance (ANCOVA) model with treatment groups (sotagliflozin 400 mg, sotagliflozin 200 mg, and placebo), randomization stratum of screening HbA1c ($\leq 8.5\%$, $> 8.5\%$), randomization stratum of mean SBP at screening (< 130 mmHg, ≥ 130 mmHg), randomization stratum of CKD stage (3A, 3B), treatment by randomization stratum of CKD stage, and country as fixed effects, and baseline HbA1c value as a covariate.

Results from each analysis will be combined using Rubin's formula, to provide the adjusted mean change in HbA1c from Baseline to Week 26 (or Week 12 for SBP) for each treatment group, as well as the between-group difference (comparing sotagliflozin 400 mg versus placebo and sotagliflozin 200 mg versus placebo) and its associated 95% confidence interval (CI).

Patients in this study have undergone sampling for plasma levels of sotagliflozin and its main active metabolite in order to perform population PK analysis. Patients may be identified as those who have no detectable levels of active study drug or metabolite in their samples (ie, Below Limit of Quantification or BLOQ). When sample analysis has been completed and the study has been unblinded, explanations for some of these patients may be found: known non-compliance or sampling occurring after treatment had been discontinued. In other cases, drug intake history relative to the randomization assignment may not be fully explained. The ITT-based analyses specified in this document provides for a conservative assessment of the efficacy data should patients have been subjected to these unexplained non-compliance findings or PK 'anomalies'. To provide a broader perspective on the impact of these apparent errors in compliance, additional sensitivity analyses of the primary efficacy endpoint and continuous efficacy endpoints may be conducted. The need to perform such analyses, their specifics, and results will be provided in the Clinical Study Report (CSR), if applicable. The analysis methods applied to the patient subpopulations defined by the occurrence of the PK anomalies (eg, exclusion of patients with PK anomalies from the ITT dataset) will include the ANCOVA model using the retrieved dropout and/or washout MI methods, and the tipping point analyses previously specified in this section.

Statistical Analysis Plan

Version: Final 3.0

Lexicon Pharmaceuticals Protocol No. EFC14837

Date of Issue: 21 November 2019

Covance Study ID:000000155205

Analysis of the primary and secondary endpoints at Week 26 as specified in Sections 2.4.4.1 and 2.4.4.2 will be repeated for these same measures at Week 52, even though Section 2.4.4.3 called for these analyses to be descriptive only. In addition, the sensitivity analysis methods described in this section will be applied to these variables at Week 52.

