#### **11.4.2.2 Analyses of secondary efficacy endpoints**

The secondary endpoints (see [Section 9.1.2](#)) will be analyzed using a similar approach to the primary efficacy endpoint with missing values imputed by control-based multiple imputation method under the missing not at random framework.

- For placebo patients, missing data will be imputed based on the placebo group data.
- For patients in the sotagliflozin group, missing data will be imputed as if the patients were on placebo group throughout the study, where all patients' measurements including the on-treatment measurements will be considered as if the measurements were from the placebo group in the imputation model.

For each of the continuous secondary endpoints, each of the complete datasets will be analyzed by an ANCOVA model with treatment (sotagliflozin 400 mg, sotagliflozin 200 mg, placebo), randomization stratum of HbA1c ( $\leq 8.5\%$ ,  $> 8.5\%$ ), randomization stratum of Screening SBP ( $<130$  mmHg,  $\geq 130$  mmHg), CKD stage at Screening (3A, 3B), and country as fixed effects, and Baseline secondary endpoint value as a covariate. Results from each complete dataset will be combined to provide the adjusted mean change from Baseline to Week 26 (or Week 12 for SBP) for each treatment group, as well as the between-group difference (comparing each sotagliflozin group versus placebo) and its associated 95% CI using appropriate contrast statements.

The categorical secondary efficacy variables of HbA1c  $<6.5\%$ ,  $<7\%$  at Week 26 will be analyzed using a Cochran-Mantel-Haenszel method stratified by the randomization stratum of Screening HbA1c ( $\leq 8.5\%$ ,  $> 8.5\%$ ), randomization stratum of Screening SBP ( $<130$  mmHg,  $\geq 130$  mmHg), and CKD stage at Screening (3A, 3B). The proportion in each treatment group will be provided, as well as the difference of proportions between sotagliflozin and placebo with associated 2-sided 95% CI. For HbA1c responders at Week 26 ( $<6.5\%$ ,  $<7\%$  respectively), all values at Week 26 will be used to determine whether a patient is a responder or not, even if they are measured after IMP

discontinuation or rescue medication use. Patients who have no HbA1c measurement at Week 26 will be treated as non-responders.

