2.4.4.2 Analyses of secondary efficacy endpoints

For continuous secondary efficacy endpoints with missing baseline observations, missing data will be imputed using MI under the assumption of missing at random (MAR). Missing data at baseline will be imputed using regression method that includes randomization stratum of HbA1c ($\leq 8.5\%$, $> 8.5\%$), randomization stratum of SBP (< 130 mmHg, ≥ 130 mmHg), randomization stratum of CKD stage (3A, 3B), and baseline value in the imputation model (sample code in Appendix B Part 1b or 2b).

Each continuous secondary efficacy endpoint ([Section 2.1.3](#)) will be analyzed using similar ANCOVA model including the measurements at baseline and endpoint (observed or imputed). The missing data at endpoint will be imputed by the retrieved dropouts & washout imputation method or by the control-based copy reference imputation method according to the method as described in [Section 2.4.4.1](#). After the imputation, each of the complete datasets will be analyzed by an ANCOVA model.

The ANCOVA model will include treatment groups (sotagliflozin 400 mg, sotagliflozin 200 mg, and placebo), randomization stratum of screening HbA1c ($\leq 8.5\%$, $> 8.5\%$), randomization stratum of mean SBP at screening (< 130 mmHg, ≥ 130 mmHg), randomization stratum of CKD stage (3A, 3B), and country as fixed effects, and the corresponding baseline value as a covariate.

Results from each complete dataset will be combined using Rubin's formula to provide the adjusted mean change from baseline to Week 26 (Week 12 for SBP) for each treatment group, as well as the between-group difference (comparing sotagliflozin 400 mg, sotagliflozin 200 mg, respectively, to placebo) and the 95% confidence interval (CI) for the between-group difference. For analyses of SBP in patients with baseline SBP ≥ 130 mmHg, randomization stratum of SBP will not be included in the ANCOVA model.

UACR will be log-transformed at patient level before analysis, and geometric means (with and without ANCOVA model adjustment), differences between treatments and 95% CIs will be back-transformed to original scale. Summary statistics will be calculated in log-scale by treatment group at each visit and back-transformed for overall population and each CKD stratum. Geometric mean and its associated percent change of UACR from baseline will be presented.

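### Read literally, SAP 1.6 adjusts the sensitivity ANCOVAs of the continuous secondary endpoints for baseline HbA1c instead of each endpoint's own baseline

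*SAP*

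**What the plan says.** The scope sentence of the added analyses in SAP 1.6 begins "The primary and continuous secondary efficacy endpoints for the overall population (combined CKD stages 3A and 3B" and goes on to the separate CKD strata, naming Week 12 for SBP. Two ANCOVA models follow.

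- Overall population: the model ends "and country as fixed factors, and baseline HbA1c value as a covariate".
- Each CKD stratum: the model ends "treatment by randomization stratum of CKD stage, and country as fixed effects, and baseline HbA1c value as a covariate".

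No sentence in Section 1.6 gives another covariate for FPG, weight, SBP or UACR. The imputation step of the same section does use the endpoint's own baseline: "The imputation models for the washout MI method will include the randomization strata and the corresponding baseline value". The pooled output is described as "the adjusted mean change in HbA1c from Baseline to Week 26 (or Week 12 for SBP) for each treatment group".

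The main analysis of the secondary endpoints is specified differently. SAP 2.4.4.2 has "and country as fixed effects, and the corresponding baseline value as a covariate", protocol 11.4.2.2 has "and country as fixed effects, and Baseline secondary endpoint value as a covariate", and SAP Appendix D also gives the baseline value of the endpoint. SAP 2.4.4.2 log-transforms UACR and removes the SBP stratum from the model for patients with baseline SBP ≥130 mmHg. The Section 1.6 models do neither.

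Section 1.6 states that its methods come on top of those elsewhere in the SAP, mostly as checks of robustness, and it applies them again at Week 52.

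**The concern.** A sensitivity analysis for missing data is informative when the imputation changes and everything else stays fixed. Under the literal text, the secondary-endpoint check changes the imputation and the covariate together. If the estimate or interval then moved, the reader could not tell which of the two was responsible.

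The second cost is precision. A change score that is not adjusted for its own baseline has a larger residual variance, and chance imbalance in that baseline stays uncorrected.

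These analyses have no obvious substitute. Appendix D lists no supportive analysis for the continuous secondary endpoints and points to Section 1.6, and the tipping-point analysis in SAP 2.4.4.1 is written for HbA1c. In the readable text (some rows of the change table are redacted), Section 1.6 is therefore the only missing-data check on these endpoints. Because the section makes its methods additional, the own-baseline rule in 2.4.4.2 does not override the covariate named there.

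**Working it through.** **1. The plan's own figure.** The only power statement (SAP 1.3, protocol 11.1) concerns HbA1c: SD 1.2%, two-sided 0.05, 130 patients per CKD stratum per arm (260 per arm overall). With SE = 1.2·√(2/n), power is Φ(difference/SE − 1.96).

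| Comparison | n per arm | Difference/SE | Power | Stated |
|---|---|---|---|---|
| 400 mg, stratum | 130 | 0.6/0.1488 = 4.03 | 98.1% | 98% |
| 400 mg, overall | 260 | 0.6/0.1052 = 5.70 | >99.9% | 99% |
| 200 mg, stratum | 130 | 0.5/0.1488 = 3.36 | 91.9% | 91% |
| 200 mg, overall | 260 | 0.5/0.1052 = 4.75 | 99.7% | 99% |

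A simulation of 400,000 trials puts the joint power of all six tests at 82.5%, against the stated minimum of 80%. The figures reproduce. None of them concerns the secondary endpoints, so the precision question needs assumptions.

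**2. Variance ratio.** Let r be the correlation between an endpoint's baseline and its value at the analysis visit. Let R² be the share of own-baseline variance already explained by baseline HbA1c and the strata. Assume equal variances s² at both times, and no further link between those terms and the visit value once own baseline is known.

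- Residual variance with own baseline in the model: s²(1 − r²).
- Residual variance of the change without it: s²[(1 − r)²(1 − R²) + 1 − r²].
- Ratio: [2 − R²(1 − r)]/(1 + r).

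With R² = 0 this is 2/(1 + r), which is the upper bound. The increase in SE, or in confidence-interval width, is the square root of the ratio minus 1.

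| r | R² = 0 | R² = 0.30 | R² = 0.36 |
|---|---|---|---|
| 0.4 | 1.43 (SE +19.5%) | 1.30 (+14.0%) | 1.27 (+12.9%) |
| 0.5 | 1.33 (+15.5%) | 1.23 (+11.1%) | 1.21 (+10.2%) |
| 0.6 | 1.25 (+11.8%) | 1.18 (+8.4%) | 1.16 (+7.7%) |
| 0.8 | 1.11 (+5.4%) | 1.08 (+3.8%) | 1.07 (+3.5%) |
| 0.95 | 1.03 (+1.3%) | 1.02 (+0.9%) | 1.02 (+0.8%) |
| 0.98 | 1.01 (+0.5%) | 1.01 (+0.4%) | 1.01 (+0.3%) |

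**3. Check by simulation.** With 260 patients per arm, five settings gave variance ratios of 1.32, 1.21, 1.21, 1.19 and 1.00, against 1.33, 1.23, 1.21, 1.16 and 1.01 from the formula. The true difference was zero, and the mean estimate was close to zero under both models, so the covariate choice brings no bias.

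**4. In terms of power.** A comparison with 90% power under own-baseline ANCOVA has a standardized effect of 1.960 + 1.282 = 3.242. At r = 0.5 and R² = 0, power becomes Φ(3.242/√1.333 − 1.960) = Φ(0.85), about 80%. At r = 0.5 and R² of 0.30 to 0.36 it is about 83-84%. At r = 0.98 and R² = 0 it is 89.7%.

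**The case against.** The strongest reply is that this is a drafting slip and not a decision. The output sentence speaks of the mean change in HbA1c and in the same breath of Week 12 for SBP, which cannot be literally right. The imputation step uses the endpoint's own baseline. The sample code in SAP Appendix B uses a generic `value0`, defined as the value at baseline. Appendix D gives own baseline for these endpoints in the same row that refers to Section 1.6. All of this stands: the programmer may well have used the right covariate. It does not remove the inconsistency, because Section 1.6 names HbA1c explicitly and does not cite the code.

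The size can also be disputed. The 12-20% figure treats the model as holding no information on the endpoint's own baseline. In fact the SBP stratum carries part of baseline SBP, and baseline HbA1c may carry part of baseline FPG. For body weight, where a very high correlation is expected, almost nothing is lost. This stands too, so the figure is only an upper bound for moderately correlated endpoints.

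A reader might infer that the robustness checks in general are weakened, including the one for the primary endpoint, or that the trial's conclusions are at risk. The documents do not support that. For HbA1c the named covariate is its own baseline. The Section 1.6 sensitivity analyses are not in the testing hierarchy of SAP 2.4.4.4. The own-baseline analyses of 2.4.4.2 are still run, and Section 1.6 repeats them at Week 52.

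**Conclusion.** The point holds as a specification error confined to the sensitivity ANCOVAs of FPG, body weight, SBP and UACR. That the text names the wrong covariate for these endpoints, against three other places in the plan, rests on the wording alone and is certain. That the analyses would be run that way is not.

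The loss of attribution matters most and needs no numerical assumption. The loss of precision ranges from negligible to moderate, depending on r and R², neither of which the documents give. It is at most about 12-20% in SE at r of 0.4-0.6, about 8-14% if R² is 0.30-0.36, and about 0.5-1% at r of 0.95-0.98. Type I error control, the sample size and the HbA1c results are unaffected. The correction should be made because it is free and because Section 1.6 is the check these endpoints rely on.

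**What to change.** In both Section 1.6 ANCOVA models, replace baseline HbA1c with the baseline value of the endpoint being analysed, on the log scale for UACR. For HbA1c this changes nothing. For the analysis of patients with baseline SBP ≥130 mmHg, drop the SBP stratum, as SAP 2.4.4.2 does; otherwise a second covariate difference from the main analysis remains. In the sentence on pooled results, refer to the adjusted mean change in the endpoint instead of in HbA1c. State that the same specification applies at Week 52 and to any PK-anomaly analyses.

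The cost is SAP wording, with no new data and no change to any sample-size figure or confirmatory test. SAP 1.6 records that the first-step analysis had already been carried out and reported for topline results, so the edit should be dated and documented as a clarification made after them. If the analyses have already been run, the report should state which baseline was used.
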